OMT Trigger Point Protocol Cover Page

Trial Name: Treating Trigger Points: Comparing Muscle Energy Techniques vs. Lidocaine Needling Technique for Pain Control and Quality of Life Measures.

NCT #: NCT05009264

Document Date: April 28, 2022

A comparison of effectiveness of muscle energy technique and dry needling injections on quality of life and pain control in treating trigger points

Introduction

Myofascial pain syndrome is one of the most common musculoskeletal disorders seen in the aging US population ^{1,2}. Its characterized by myofascial trigger points (MTPs) which were first defined by Simons et al. (1999) as hyperirritable nodules in a taut band of skeletal muscle, associated with pain on manual stretching, contraction, or stimulation of the muscle³. Trigger points are further classified into active and latent based on their clinical features ⁴. Active MTPs are characterized by spontaneous pain at rest with referred pain on palpation whereas latent MTPs produce pain on palpation in addition to restriction of range of motion ^{2,4-7}.

Currently, there are a variety of treatment options for MTPs including lidocaine injections, dry needling, osteopathic manipulative treatment, massage therapy, ultrasound therapy etc. There has been a large amount of research investigating the safety and efficacy of dry needling and lidocaine trigger point injection techniques in treating MTPs. The results suggest that dry needling and lidocaine injections were both equally effective in reducing symptoms associated with MTPs as it was the mechanical disruption of the taut fibers due to the needle effect and the depth of adequate penetration that resulted in pain reduction more than the substance actually delivered into the muscle ⁸⁻¹³. Some authors also suggested the importance of a local twitch response (LTR); which is an observable contraction of the taut part of muscle band upon stimulation, during dry needling technique as being pertinent for maximum effectiveness. ^{8,14}However, a recent systemic review found that LTR during dry needling treatment was unnecessary and not required for management of myofascial pain syndrome ¹⁵.

On the other hand, there has been fewer research investigating the effects of manual treatment on trigger points. Travell and Simons initially treated trigger points with ischemic compression but later changed their recommendation to applying gentle digital pressure to trigger points ¹⁶. A recent study done on traction-compression-stretch technique compared with ischemic compression showed some, albeit minor, increased outcome measures (pain pressure threshold) warranting clinical investigation ⁶. (We can use their comparative model and statistics since it would be similar to our concept) Another study compared active release and muscle energy techniques in treating latent trigger points of the upper trapezius and found that both techniques were equally effective in increasing cervical range of motion and decreasing pain and upper trapezius thickness⁷. Other studies have also shown interest in similar osteopathic manipulative techniques such as counterstrain, myofascial release, facilitated positional release and high velocity-low amplitude thrust techniques in treating trigger points^{3,16-18}.

Studies have showed that the upper trapezius is one of the most common muscles affected by myofascial pain syndrome ^{19,20} leading to referred pain manifesting as headaches and stiff neck.

There is no consensus as to which treatment method is superior, with the decision to treat in a certain way/technique largely based upon the training received by the individual physician rather than the characteristics of the trigger point itself. There are currently no studies evaluating the efficacy of the various treatment options specifically osteopathic manipulative treatment vs. trigger point injections. Thus, the intention of the present study was to determine the efficacy rates of muscle energy techniques vs. dry needling in treating MTPs in the upper trapezius region.

Study Objective

The primary aim of this study is to observe whether osteopathic manipulative treatment or traditional lidocaine/dry needling technique is more efficacious or non-inferior and similar in treating myofascial trigger points in the upper trapezius region as it relates to quality of life and improvement in pain scores.

Study Design

The study is a prospective cohort study comprised of participants between ages 25-75 presenting to Atlanticare Regional Medical Center interventional pain department and Philadelphia College of Osteopathic Medicine OMM Clinic between April 2021 and May 2021 with trigger point in the upper trapezius muscle. It is expected that approximately 60 patients will be enrolled to produce approximately 50 evaluable subjects.

Inclusion Criteria: The subjects will only be recruited into the study if they have met all the following criteria:

- Ages between 25 and 60 years.
- Previous or current diagnosis of MTrP in the upper trapezius region according to the criteria set by Simons et al.³
- 1 active/latent MTrP in the upper trapezius region

The diagnostic criteria to establish myofascial trigger point is adopted from Travell and Simons³ and include:

1. Presence of palpable taut band in the skeletal muscle
2. Presence of hypersensitive tender spot in the taut band
3. Presence of local twitch response upon stimulation of the taut band
4. Reproduction of referred pain upon palpation
5. Presence of spontaneous referred pain pattern

Exclusion criteria: Any subject that exhibits any of the following criteria will be excluded from the study:

- Pregnancy or immunocompromise
- Fever/infection
- Previous history of whiplash injury
- Previous history of cervical surgery, cervical radiculopathy, or myelopathy
- Severe disc or cervical lesion
- Evidence of cognitive deficit
- Degenerative or inflammatory disease of the cervical spine or shoulder, fibromyalgia, or neuromuscular diseases
- Use of medications (anticoagulants, anti-inflammatory etc.) or illicit drug use (1 week prior to treatment or follow up)
- Received treatment for MPS a month before the study recruitment

All the patients of interest that present to AtlantiCare Regional Medical Center pain clinic and Philadelphia College of Osteopathic Medicine OMM Clinic that meet the relevant inclusion and exclusion criteria will be invited to participate in this study. The subjects will be informed of the purpose of the study and asked for informed consent. If recruited into the study, they will be administered a pre-intervention survey. Subjects will then be managed according to standard of care by their point of care physician. Following the intervention they will be administered a post-intervention survey immediately following the intervention and one-week post.

Pre-intervention assessment will include pain intensity/evaluation using point system and quality of life measured by the neck disability index.

Post-intervention assessment will include pain intensity/evaluation using point system, administered immediately after the intervention, and one week following the intervention using phone survey or online survey depending on patient preference and comfort.

Intervention

Group1 (PCOM): Will receive the muscle energy technique; trigger point isolated followed by post isometric relaxation muscle energy technique

Group 2 (AtlantiCare Regional Medical Center): Will receive lidocaine injection technique

Outcome Measures

1. *Pain intensity*; measured using a point system; where 0 = no pain and 10 = maximum pain. Although this is a subjective measurement by the patient, we are interested in looking at the difference between pre- and post-intervention pain intensity ratings.
2. *Quality of Life*; measured by the Neck disability Index²² which is used to evaluate neck and upper extremity function. The total score is divided by number of answered questions, subtracted 1 and multiplied by 25, in a scale score that range from 0 to 100, with higher scale scores indicating more disability.

Neck Disability Index score rating²³:

- 0-4 points (0-8%) : no disability,
- 5-14 points (10 – 28%) : mild disability,
- 15-24 points (30-48%) : moderate disability,
- 25-34 points (50- 64%) : severe disability,
- 35-50 points (70-100%) : complete disability

Procedure

Patients that consent to the study and are eligible following the inclusion & exclusion criteria will be recruited into the study. They will fill out the pre-intervention survey in the room. Once the survey is completed, the patient will be placed in a seated position and using palpation, the examiner will identify

the MTrP according to the criteria set by Simons et al. Following the subjective pre-assessment, the intervention will be performed.

Group 1 will be primarily focused on patients from the OMM clinic at PCOM. Patients will be administered muscle energy technique of post isometric relaxation as per the Atlas of Osteopathic Techniques on the symptomatic upper trapezius without treatment of surrounding structures by the osteopathic attending physician.

Group 2 will be comprised of patients from AtlantiCare Regional Medical Center pain clinic and will be administered trigger point dry needling and lidocaine injection. The treatment will be administered by the pain clinic attending physician. After application of a coolant to numb the area, the isolated trigger point will be penetrated using a 30-gauge needle, to a depth adjusted depending on the patient, into the subcutaneous tissue. The patient will be warned about possible unpleasant sensations and mild pain associated with contraction of the tight band of muscle. Multiple needle insertions will be attempted to achieve MTrP inactivation, with the needle being withdrawn to the subcutaneous layer but not from the skin during each insertion, approximately lasting for 1-2 minutes ^{26,27}. Once the fascial tension is relieved, 0.5% lidocaine will be injected, and the needle will be withdrawn from the skin. The procedure will be terminated with hemostasis achieved.

Once the intervention is completed, the patient will be asked about the reduction in pain following the intervention and administered the post intervention survey. A week after the intervention, they will be called/mailed to ask about their pain intensity using the same post intervention survey by the medical students.

Safety Management:

Patients are free to withdraw from the study at any time should they choose to. Since the study procedures are not greater than minimal risk, adverse events are not expected. If any serious adverse effects or unaccounted events may occur, they will be reported to the IRB and patients will be discontinued from the study. The data from withdrawn patients will not contribute to the study statistics.

Data Analysis

The data will be analyzed using SPSS version 27.0 for Windows (IBM Corp. Released 2020. IBM SPSS Statistics for Windows, Version 27.0. Armonk, NY: IBM Corp). Values of interest include measures of central tendency, i.e. mean, standard deviation, normal distribution, confidence intervals etc. To be considered a statistically significant finding, the alpha level will be set at 0.05. A descriptive analyses of the outcome variables will be conducted to compare between the intervention groups. The homogeneity of sociodemographic data (age, sex, comorbid conditions) and treatment groups will be analyzed using the Fischer test and Pearson chi square test, respectively.

The outcome measures, reported pain and quality of life, will be analyzed separately using univariate analyses. The differences between the treatment groups across time periods will be analyzed. A two-factor analysis of variance (ANOVA) will be performed for each dependent variable to determine the

difference between treatment groups at the different time points (before the intervention, immediately after the intervention, and a week post the intervention). A 2 x 3 mixed factor design will be used in order to evaluate the between subjects data (intervention type) across the repeated measures (three time periods).

Study Administration

The primary records of data will be in form of pre- and post- intervention surveys. Each survey will contain a random code to link the patient to the survey data and that list will be kept separate from the surveys. All physical copies of data will be stored primarily at [name] office under lock and key with key access only to them. Data collected through Atlanticare pain clinic will be maintained through one set of copies which will be stored at [name] office under lock and key with key access only to them. Data collected through PCOM will be maintained through one set of copies which will be stored at [name] office under lock and key with key access only to them. Surveys administered through email will be sent through a secure link and all online data will be encrypted with access only to principal investigators and research personal. All data obtained through email will be stored on the principal investigator's computer which is password protected. All data and records generated during this study will be kept confidential in accordance with Institutional policies and HIPAA on subject privacy and the investigator and other site personnel will not use the data and records for any purpose other than conducting the study. The identifiers and other data will be destroyed 5 years after study completion in compliance with the Atlanticare Regional Medical Center data retention policy.

References

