- 1 active/latent MTP in the upper trapezius region

The diagnostic criteria to establish myofascial trigger point is adopted from Travell and Simons³ and include:

1. Presence of palpable taut band in the skeletal muscle
2. Presence of hypersensitive tender spot in the taut band
3. Presence of local twitch response upon stimulation of the taut band
4. Reproduction of referred pain upon palpation
5. Presence of spontaneous referred pain pattern

Exclusion criteria: Subjects that exhibited any of the following criteria were excluded from the study:

- Pregnancy or immunocompromise
- Fever/infection
- Previous history of whiplash injury
- Previous history of cervical surgery, cervical radiculopathy, or myelopathy
- Severe disc or cervical lesion
- Evidence of cognitive deficit
- Degenerative or inflammatory disease of the cervical spine or shoulder, fibromyalgia, or neuromuscular diseases
- Use of medications (anticoagulants, anti-inflammatory etc.) or illicit drug use (1 week prior to treatment or follow up)
- Received treatment for MPS a month before the study recruitment

All eligible participants were screened at their respective clinic with the above criteria. Subjects who agreed to participate in the study provided informed consent. At this time, they were given a demographic survey and pre-intervention survey. This survey included a standard pain intensity evaluation using a 0-10 pain scale and a quality-of-life assessment measured by the neck disability index. After enrollment and pre-intervention assessment, the appropriate intervention was administered to

the patient; patients at the Philadelphia OMM clinic received muscle energy treatment, while patients at the Atlanticare Pain Management clinic received lidocaine with dry needling.

Participants presenting to the PCOM OMM clinic were treated with the muscle energy technique of post isometric relaxation on the symptomatic upper trapezius by a board-certified osteopathic physician. After placing patient in a supine position, the shoulder on the affected side was stabilized with one arm. Using the other arm, the head was sidebent contralaterally and rotated ipsilaterally until the restriction barrier was encountered. This position was then maintained for 10 seconds while a normal respiratory rhythm was maintained. After 10 seconds the position was extended further into the barrier and held for 30 seconds and process repeated.

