Participants presenting to the Atlanticare Pain Management clinic received a lidocaine injection after dry needling into the location of the MTP by a board-certified pain management physician. First, the upper trapezius MTP was identified and isolated. After application of a coolant to numb the area, the isolated trigger point was penetrated using a 30-gauge needle, to a depth adjusted depending on the patient, into the subcutaneous tissue. The duration of treatment was approximately 1-2 minutes. Once the myofascial tension was relieved, 2 mL of 0.5% lidocaine was injected into the MTP.

After their respective interventions, the patient completed an immediate post-intervention survey, consisting of a 0-10 pain scale. Finally, approximately 7-10 days after the intervention, patients were contacted by telephone to complete the one-week post-intervention survey consisting of a 0-10 pain scale.

Outcome Measures

Pain intensity; measured using a point system; where 0 = no pain and 10 = maximum pain. Although this is a subjective measurement by the patient, we are interested in looking at the difference between pre- and post-intervention pain intensity ratings.

Data Analysis

The data was analyzed using R software. Values of interest include mean, median, standard deviation, normal distribution, confidence intervals etc. Intergroup and intra-group comparisons were conducted using independent t-tests and paired t-tests, respectively. Alpha level is set at 0.05 and p values less than that will be considered statistically significant. A descriptive analysis of the outcome variables was conducted to compare between the intervention groups. The homogeneity of sociodemographic data (age, sex, comorbid conditions) and outcome measures were analyzed using the Fischer test and Pearson chi square test, respectively.

The outcome measures were analyzed separately in both treatment groups. The contrast between the treatment groups was analyzed. A univariate analysis of the difference of the outcome variables at the different time points (before the intervention, immediately after the intervention, and a week post the intervention) were obtained through the student *t*-tests. A multivariate analysis was carried out using multiple logistic regression models with age, sex, and intervention group (Injection = 0, OMM = 1) factored as the independent variables.

Results

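### The medication exclusion reaches into the week before follow-up, so as written it can drop treated patients for a reason that depends on treatment failure

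*Protocol*

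**What the plan says.** The exclusion list under Study Design in the protocol contains "Use of medications (anticoagulants, anti-inflammatory etc.) or illicit drug use (1 week prior to treatment or follow up", and the SAP repeats the criterion. The protocol's lead-in gives the consequence: "Any subject that exhibits any of the following criteria will be excluded from the study". The SAP reports it as done: "Subjects that exhibited any of the following criteria were excluded from the study".

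On timing, the protocol's Study Design says "they will be administered a post-intervention survey immediately following the intervention and one-week post". The SAP says "approximately 7-10 days after the intervention, patients were contacted by telephone to complete the one-week post-intervention survey consisting of a 0-10 pain scale". That is the SAP's full description of the one-week contact, and it includes no question about medication.

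Under Safety Management the protocol adds: "The data from withdrawn patients will not contribute to the study statistics". The SAP's Results section calls its analysis per protocol. Neither Data Analysis section says how medication taken after treatment is handled, and neither plans a sensitivity analysis for it.

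**The concern.** An eligibility criterion should be settled before treatment. The follow-up part of this one can only be met afterwards, so its only possible effect is on patients already treated. The outcome is pain, the named drugs include anti-inflammatories, and continuing pain is an obvious reason to take one. Removal can therefore depend on the outcome: patients who did badly are more likely to go, and the mean reduction among those left looks better than the mean among all treated.

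The effect need not be equal in the two groups. The SAP's Table 1 shows baseline pain of 2.76 (OMM) against 7 (lidocaine). All 21 OMM patients are aged 20-29, and 8 of the 10 lidocaine patients are over 60. Medication use could differ between such groups for reasons unrelated to treatment, so the comparison could move either way.

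**Working it through.** **1. How much of the post-treatment period the window covers.** With contact on day 7 it covers 7/7 = 100%. With contact on day 10 it covers 7/10 = 70%. So it is all or most of the period, not always the whole.

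**2. The SAP's patient accounting.** Results gives 21 OMM + 10 lidocaine = 31 enrolled, and 1 lidocaine patient lost at one week: 31 - 1 = 30. Table 2 has 21 + 9 = 30, so the figure is reproduced. The reported t and p values can be checked against the number of pairs (two-sided p):
- OMM: t = 2.10 and 2.68 on 20 df give p = .049 and .014 (reported .048 and .014), so 21 pairs at both times.
- Lidocaine, immediate: t = 1.17 on 9 df gives .272 (reported .27), so 10 pairs.
- Lidocaine, one week: t = 2.16 on 8 df gives .063 (reported .062), so 9 pairs. The printed 20 df would give .043.

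Among the 31 counted as enrolled, there is no room for a removal because of medication.

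**3. What the rule would do if applied (illustration).** Inputs from the SAP's Results: mean one-week reductions of 2.76 - 1.81 = 0.95 (OMM) and 7 - 4 = 3.0 (lidocaine). SD of change = mean × √n / t:
- OMM: 0.95 × √21 / 2.68 = 1.62
- Lidocaine: 3.0 × √9 / 2.16 = 4.17

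Assumptions: changes are normal, the reported means are unselected, and a fraction f = 10-30% is removed. The documents give no such rate.

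*Extreme case: exactly the worst responders are removed.* The mean rises by SD × φ(z)/(1 - f), where z is the 1 - f quantile and φ the normal density. The multiplier is 0.195 at f = 10% and 0.497 at f = 30%.
- Lidocaine: 3.0 + 4.17 × (0.195 to 0.497) = 3.8 to 5.1
- OMM: 0.95 + 1.62 × (0.195 to 0.497) = 1.3 to 1.8

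*Mild case: below-median responders are twice as likely to be removed.* The removal rates are 4f/3 below the median and 2f/3 above it, and the two halves have means ∓0.798 SD. The rise is SD × 0.798 × (f/3)/(1 - f), with multiplier 0.030 at 10% and 0.114 at 30%.
- Lidocaine: 3.1 to 3.5
- OMM: 1.0 to 1.1

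**4. Direction of the between-group effect.** Here the assumption is reversed: the reported means are taken as already selected, and the removed patients are assumed to have had zero change. For f, use the loss implied by the protocol's statement that "It is expected that approximately 60 patients will be enrolled to produce approximately 50 evaluable subjects": 1 - 50/60 = 16.7%. The protocol does not say what causes that loss. All-treated reductions would be 0.95 × 5/6 = 0.79 (OMM) and 3.0 × 5/6 = 2.50 (lidocaine), so the within-group figures would be inflated by 0.16 and 0.50. The difference in reduction as reported is 3.0 - 0.95 = 2.05. Among all treated patients it would be:

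| Removal in | Difference |
|---|---|
| both groups | 2.50 - 0.79 = 1.71 |
| OMM only | 3.00 - 0.79 = 2.21 |
| lidocaine only | 2.50 - 0.95 = 1.55 |

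The reported difference could be too large or too small, so the direction is not fixed.

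**The case against.** The strongest reply is that the criteria are applied before treatment. In the protocol, patients who meet them are invited and recruited. In the SAP, patients are screened, then consent, then are treated. No sentence says that a treated patient who later takes a drug is dropped. The rule on withdrawn patients' data stands in a paragraph about voluntary withdrawal and serious adverse events. With no medication question described, the rule may never have been enforced. All of this stands as a description of the documents. It does not rescue the rule, because read as pre-treatment eligibility only, the reference to follow-up has no meaning. If the rule was not enforced, the ratings of medication users are mixed in without being identified, and the same fix applies.

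A reader might infer that non-responders were in fact removed and that the reported pain reductions are biased. The documents do not support that. The one post-enrolment exclusion is given as a loss to follow-up, and the accounting closes without any other. The SAP gives no exclusion counts by criterion, so it does not show whether the 31 were counted after any removal under this rule. That is a gap in reporting, not evidence of a removal.

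It is also fair to say that step 3 starts from the reported means as if no one had been removed. It therefore shows what the rule could do, not an error in this trial's figures.

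**Conclusion.** The point holds as a defect in a stated rule. As written, the criterion permits exclusion after treatment for a reason linked to outcome, and nothing in either analysis section offsets it. The risk is an inflated one-week within-group reduction and a between-group comparison distorted in an unknown direction. The immediate post-treatment rating precedes any such medication use and is affected only if the whole patient is dropped.

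The size is illustrative. It depends on the assumed 10-30% removal, on normal changes, and on how strongly removal tracks poor response. The shift ranges from small (OMM 0.95 to 1.0-1.1 in the mild case) to large (lidocaine 3.0 to 3.8-5.1 in the extreme case). No bias in the reported result is demonstrated.

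**What to change.** In the exclusion lists of both documents, delete the reference to follow-up, so that for deciding who is analysed the medication criterion applies at enrolment only. State that every treated patient with a rating stays in the primary analysis, whatever they took. Record medication use at the one-week contact and add one sensitivity analysis that flags users.

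The SAP dates recruitment to November 2021 to February 2022 and already reports results, so a survey question may no longer be possible. In that case, report the number excluded under this criterion, including zero if that is the answer, and restore any such patients to the analysis.

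The cost is a short deletion in each document, one survey question where collection is still open, and one extra analysis. The small downside is that the one-week rating then reflects treatment plus any medication taken, and the SAP should say so. The change concerns who is analysed, not what patients may take.

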We specifically note that this is a suitable treatment modality for all physicians, both osteopathic and allopathic, as we merge our skill sets over time in a unified manner. As mentioned, the training of a physician usually dictates the management decisions regarding MTP treatment. This study was conducted in a post graduate training institution that has multiple specialty programs with osteopathic recognition. In the single accreditation system, collaborating with allopathic physicians and exposing allopathic residents to osteopathic treatment options was viewed an advancement for patient centered care and osteopathic awareness. As more allopathic physicians expand their skill sets and complete OMT courses, demonstrating the efficacy of a common treatment modality compared to OMT will assist with treatment choice. Comparable efficacy of both options will help patients choose the option that best meets their needs and physicians choose the option that best augments their skill set.

Being a pilot study, we anticipated a considerable degree of limitations throughout the study. Limitations include but are not limited to low sample size, majority female participants, and substantial difference in mean age between the two groups. Additionally, the OMT intervention group had a significantly lower mean pre-intervention pain level compared to the lidocaine group which made it difficult to do a true comparative analysis between groups. However, as a pilot study, demonstration of OMT non-inferiority compared to a standard treatment modality, creates a stepping stone for future research to investigate the comparative efficacy of OMT on a larger scale and we therefore anticipate future trials with larger number of participants to demonstrate more significant data and results.

Conclusion

Based on our study, OMT has comparable value with lidocaine injection technique as a treatment modality for active TrPs in the upper trapezius region. Both techniques demonstrate considerable decrease in pain intensity from baseline and thus it allows for increased collaboration between osteopathic and allopathic practitioners to promote patient centered care.

References

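### Treatment is fully confounded with clinic and operator specialty, which the SAP's limitations omit while it still claims equal efficacy, non-inferiority and comparable value

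*Protocol*

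**What the plan says.** **Allocation.** The protocol's Intervention section reads "Group1 (PCOM): Will receive the muscle energy technique; trigger point isolated followed by post isometric relaxation muscle energy technique" and "Group 2 (AtlantiCare Regional Medical Center): Will receive lidocaine injection technique". Its Procedure section is slightly looser for the first group: "Group 1 will be primarily focused on patients from the OMM clinic at PCOM". The SAP's Study Design section describes what was done: "patients at the Philadelphia OMM clinic received muscle energy treatment, while patients at the Atlanticare Pain Management clinic received lidocaine with dry needling". Neither document describes randomisation, matching, or any patient receiving the other clinic's treatment.

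**Operator.** The SAP says the Philadelphia patients were "treated with the muscle energy technique of post isometric relaxation on the symptomatic upper trapezius by a board-certified osteopathic physician". It assigns the AtlantiCare injections to a board-certified pain management physician.

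**Analysis.** The multivariable model in the SAP's Data Analysis section contains age, sex and intervention group. It has no term for clinic, operator or baseline pain, and the Results report no output from it. The between-group result reported over time is a mixed-design ANOVA interaction, F(1.65, 56) = 3.90, p = .034.

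**Limitations and claims.** The SAP Discussion begins its list "Limitations include but are not limited to low sample size, majority female participants". It goes on to the age difference and the lower baseline pain in the muscle energy group, and says the latter hampered a true comparison. Clinic, operator and allocation by site do not appear. The Discussion also asserts equal efficacy and a demonstration of non-inferiority, and the Conclusion says "OMT has comparable value with lidocaine injection technique".

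**The concern.** The protocol's objective asks whether one treatment is more efficacious than, or non-inferior to, the other. That question is about treatments. The observed contrast is between patients treated at one clinic by one specialty and patients treated at another clinic by another specialty. Anything that differs between the clinics enters the contrast at full weight, and the data cannot remove it.

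A reader of the Conclusion would take away that the two treatments perform about equally. The design does not identify that statement, and the limitations do not tell the reader why.

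**Working it through.** **1. Reproduce the SAP's between-group result.** With 30 patients in two groups and three time points, the uncorrected error df are (30 - 2) x 2 = 56. The Greenhouse-Geisser numerator df of 1.65 implies error df of 1.65 x 28 = 46.2. The upper tail of F = 3.90 is 0.0345 on (1.65, 46.2), 0.0332 on the printed (1.65, 56), and 0.0260 on (2, 56). The reported .034 is reproduced with the corrected df; the printed 56 is the uncorrected value. Table 2's Total rows also follow from its group rows (for example, baseline 4.03, SD 2.96).

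A significant interaction says that the two groups' time courses differ. It is not evidence of equality.

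**2. Can a treatment effect be separated?** Code treatment, clinic and operator specialty as 0/1 for each of the 30 analysed patients. The three columns are identical. A model with an intercept and these three terms has 4 columns and rank 2, so only their sum is estimable.

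**3. Age (SAP Table 1).** Ages 20-29: 21/21 muscle energy, 1/10 lidocaine. Over 60: 0/21 and 8/10. The Fisher exact p for 20-29 against older is C(10,1)/C(31,9) = 10/20,160,075 = 5e-7. One lidocaine patient lies in the muscle energy group's age band, so adjustment for age has almost no support. Sex is balanced: 5/21 and 2/10 male, Fisher p = 1.0.

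**4. Baseline pain (SAP Table 2).** Muscle energy 2.76 (SD 1.84, n = 21); lidocaine 7.00 (SD 3.04, n = 9).
- Gap: 7.00 - 2.76 = 4.24 points.
- Pooled SD: sqrt[(20 x 1.84² + 8 x 3.04²)/28] = 2.25, so the gap is 4.24/2.25 = 1.9 SD. Welch p = 0.003.
- Mean reductions in the Results text: muscle energy 0.90 (immediate) and 0.95 (one week); lidocaine 0.40 and 3.00. The baseline gap exceeds all four.

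**5. What baseline adjustment would do at one week.** The raw difference, muscle energy minus lidocaine, is 1.81 - 4.00 = -2.19. With an assumed common baseline slope b, the adjusted difference is -2.19 + 4.24b.

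| Assumed b | Adjusted difference |
|---|---|
| 0 | -2.19 |
| 0.5 | -0.07 |
| 1 | +2.05 |

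The sign depends on the slope assumed.

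**6. How precise is the difference in change?** Change SDs are back-calculated from the reported t values, treating these as paired tests. The Results call them independent-samples tests. For lidocaine at one week they print 20 df with p = .062, but t = 2.16 gives p = .063 on 8 df and .043 on 20 df, so 8 df is assumed.
- One week: SDs are 0.95 x sqrt(21)/2.68 = 1.62 and 3.00 x sqrt(9)/2.16 = 4.17. Difference in reduction 0.95 - 3.00 = -2.05; SE = sqrt(1.62²/21 + 4.17²/9) = 1.43; approximate 95% CI -5.3 to +1.2 (Welch, 9.1 df).
- Immediate: SDs are 0.90 x sqrt(21)/2.10 = 1.96 and 0.40 x sqrt(10)/1.17 = 1.08. Difference 0.90 - 0.40 = +0.50; approximate 95% CI -0.6 to +1.6.

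Even ignoring the confounding, the one-week interval allows a reduction about 5 points smaller with muscle energy. Without a margin, no interval can establish non-inferiority.

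**The case against.** The strongest defence is that the study is openly a prospective cohort and a pilot. It discloses the age difference and the baseline-pain difference, admits that the latter made comparison difficult, and leaves comparative efficacy to larger trials. Its list of limitations is explicitly open-ended. Operator specialty can also be seen as part of each treatment package, because both documents say that physician training largely determines which technique is used.

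Much of this stands:
- A reader might infer that the SAP conceals the difference in patient populations. It does not: age and baseline pain are both named.
- A reader might infer that patient characteristics are as completely separated as clinic is. They are not: sex is balanced and one lidocaine patient is in the younger age band.
- A reader might suppose that different referral routes explain the gap. Neither document describes referral.
- The figures for age and baseline pain measure disclosed imbalances. Nothing in the documents sizes a further clinic or operator effect.
- Operator specialty is less clearly a confounder than clinic.

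What does not stand is the inference from these points to the claims made. An open-ended list does not tell the reader that treatment was allocated by clinic. Cohort or pilot status permits description, not equal efficacy or demonstrated non-inferiority. The protocol's looser wording for the first group does not help, because the SAP shows no mixing.

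**Conclusion.** The point holds and affects the main conclusion. Treatment coincides completely with clinic and operator specialty, so a separate treatment effect is not estimable from these data. The equal-efficacy, non-inferiority and comparable-value statements are unsupported by the design, by any stated margin, or by the interaction test. The Results statement on sociodemographic balance contradicts Table 1, and also the Discussion, which calls the age difference substantial.

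The aliasing rests only on the allocation as described. The slope range and the confidence intervals rest on the assumptions stated with them and serve as illustration.

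Two further readings go too far. A reader might take p = .034 as a pure difference between clinics; under complete aliasing that label is no better identified than a treatment effect. Nor do the data show that either treatment is superior or ineffective.

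**What to change.** In the SAP:
1. Delete the equal-efficacy, non-inferiority and comparable-value claims from the Discussion and Conclusion.
2. Add allocation by clinic, and by operator specialty, to the limitations, and say that no adjustment on these data can remove it.
3. Correct the Results statement of no significant sociodemographic difference so that it agrees with Table 1.
4. Describe the group-by-time result as a combined clinic-plus-treatment contrast.
5. Report the change in pain within each clinic's pathway as descriptive and uncontrolled, open to regression to the mean and natural recovery.

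If the objective is restated in these terms, label the restatement post hoc, because the SAP already contains results.

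The cost is rewording and a weaker conclusion. The cohort design stays, and no new patients, staff or data are needed.
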